### ***5.1.1 Special Circumstances for Informed Consent***

Incapacitated individuals, defined as persons who are mentally ill, mentally handicapped, or individuals without legal authority, are excluded from the study population. Individuals under the age of 18 or age of legal consent are excluded from the study population. Pregnant or breastfeeding women are excluded from the study population.

Individuals unable to read or write may be enrolled in this clinical investigation. Informed consent will be obtained through a supervised oral process. An independent witness will be present throughout the Informed Consent process. The written Informed Consent form and any other information will be read aloud and explained to the prospective subject or his/her legally acceptable representative and either will sign and personally date the Informed Consent form. The witness will also sign and personally date the Informed Consent form attesting that the information was accurately explained and that informed consent was freely given.

### ***5.1.2 Enrollment of Medicare Beneficiaries (U.S. Subjects Only)***

This clinical investigation will enroll appropriate Medicare beneficiaries that qualify based on the inclusion and exclusion criteria set forth in the trial. The investigational device exemption (IDE) clinical trial adheres to all standards of Medicare coverage requirements set forth by CMS's IDE and clinical trial coverage policies. The Risk Analysis section of this CIP (see **Section 17**) describes how all enrolled subjects, including Medicare beneficiaries, may be affected by the device under investigation.

Subjects enrolled in the clinical investigation are expected to be consistent with the Medicare population based on demographic characteristics and cardiovascular risk factors, therefore, the clinical investigation results are expected to be generalizable to the Medicare population.

## **5.2 Eligibility Criteria**

### ***5.2.1 General Eligibility Criteria***

Assessment for general eligibility criteria is based on medical records at the site and interview with a potential subject. Clinical and laboratory tests used to assess eligibility shall be per site standard.

If a specific test required to determine subject's eligibility is not included in a site's standard tests, the test must be performed after written informed consent has been obtained from the subject.

If any of the required screening assessments are conducted as part of standard of care prior to obtaining written informed consent, it is acceptable to provide the results of these previously performed tests for purposes of screening after the subject has consented to participate in the trial. Subjects must meet all of the inclusion criteria to be considered for the clinical trial. If any of the exclusion criteria are met, the subject is excluded from the clinical trial and cannot be registered.

If subjects are registered into the clinical investigation and are later found to have met exclusion criteria or not all inclusion criteria, these subjects will continue follow-up in the clinical investigation and will be included in the analysis population.

**Note:** Roll-in subjects must also meet the eligibility criteria listed below.

### **5.2.2 Inclusion Criteria**

Subjects must meet all of the following inclusion criteria to participate in the trial:

1. Symptomatic, moderate-to-severe or severe mitral regurgitation (MR  $\geq$  Grade III per American Society of Echocardiography criteria), or severe mitral annular calcification (MAC), where a transcatheter therapy is deemed more appropriate than open surgery by the local site heart team.

**Note:** MR and MS severity must be determined by assessment of a qualifying transesophageal echocardiogram (TEE) and transthoracic echocardiogram (TTE), obtained within 120 days prior to subject consent, and must be confirmed by the Echocardiography Core Laboratory.

**Note:** Patients with severe MAC must have symptomatic mitral valve disease associated with MR $\geq$  Grade III, or severe mitral stenosis (MS), or both moderate MR and moderate MS as assessed by the Echocardiography Core Laboratory.

2. NYHA Functional Classification  $\geq$  II (if Class IV, patient must be ambulatory).
3. The local site heart team determines that the subject has been adequately treated per applicable standards for coronary artery disease (e.g., revascularization), left ventricular dysfunction (e.g., cardiac resynchronization therapy) and heart failure (e.g., GDMT). The SEC must concur that the subject has been adequately treated.
4. The local site heart team and the SEC concur on the intended study cohort for the subject.

**Randomized cohort:** Eligibility for this cohort is limited to subjects where the local site heart team deems the mitral valve anatomy is suitable for TEER and are within approved MitraClip indications, which must be confirmed by experienced MitraClip operators within the SEC. Subjects with primary MR must be at prohibitive surgical risk, while subjects with secondary MR must be symptomatic despite maximally-tolerated guideline-directed medical therapy and meet the MitraClip Indications for Use.

**Non-repairable cohort:** Eligibility for this cohort is limited to subjects where the local site heart team deems the mitral valve anatomy is not suitable for TEER with MitraClip or does not meet MitraClip indications, which must be confirmed by experienced MitraClip operators from the SEC.

**Severe MAC cohort:** Eligibility for this cohort is limited to subjects where the local site heart team deems the degree of MAC renders the subject unsuitable for mitral valve surgery.

**Severe MAC CAP cohort:** Eligibility for this cohort is identical to the original Severe MAC cohort.

5. Age 18 years or older at time of consent.
6. Subject has been informed of the nature of the trial and agrees to its provisions, including the possibility of randomization to the Control group, complying with trial required testing, medications, and follow-up visits, and has provided written informed consent.

### **5.2.3 *Exclusion Criteria***

Subjects must not meet any of the following exclusion criteria to participate in the trial:

1. Mitral valvular vegetation or mass.
2. Left Ventricle or Left Atrium thrombus.
3. Chest condition that prevents transapical access.
4. LVEF less than 25% assessed by the site based on a TTE obtained within 120 days prior to subject consent.

**Note:** LVEF will be principally based on TTE and confirmed by the Echocardiography Core Laboratory.

5. LVEDD > 7.0 cm assessed by the site based on a TTE obtained within 120 days prior to subject consent.

**Note:** A qualifying LVEDD must be confirmed by the Echocardiography Core Laboratory.

6. Prior surgical or interventional treatment of mitral valve involving implantation of prosthetic material (e.g. valve repair or replacement, or MitraClip).
7. Mitral pathoanatomy and LVOT anatomy deemed not suitable for Tendyne transcatheter mitral valve implantation.
8. Aortic valve disease requiring surgery or transcatheter intervention.
9. Tricuspid valve disease requiring surgery or transcatheter intervention.
10. Severe tricuspid regurgitation or severe right ventricular dysfunction.
11. Any surgical or interventional procedure within the period of 60 days prior to or planned procedure 60 days following subject registration.
12. Implant or revision of CRT device within 90 days prior to intended subject registration.
13. Myocardial infarction within 30 days prior to intended subject registration.
14. Symptomatic, unresolved multi-vessel or unprotected left main coronary artery disease (e.g., active ischemia) requiring stenting or CABG.
15. CVA within 6 months prior to intended subject registration.
16. Unresolved severe symptomatic carotid stenosis (> 70% by ultrasound).

17. Cardiogenic shock or hemodynamic instability requiring inotropes or mechanical support devices at the time of planned implant procedure.
18. Hypertrophic or restrictive cardiomyopathy, or constrictive pericarditis.
19. Any of the following: leukopenia, acute anemia, thrombocytopenia, history of bleeding diathesis, or coagulopathy if cannot be adequately treated.
20. History of endocarditis within 6 months of planned implant procedure.
21. Active systemic infection requiring antibiotic therapy.
22. Known hypersensitivity or contraindication to procedural or post-procedural medications (e.g., contrast solution, anti-coagulation or antiplatelet therapy) that cannot be adequately managed medically.
23. Subjects in whom TEE is contraindicated or high risk.
24. Known hypersensitivity to nickel or titanium.
25. Subject is undergoing hemodialysis due to chronic renal failure.
26. Subject has pulmonary arterial hypertension (fixed PAS >70mmHg).

**Note:** If PAS > 70mmHg, site must provide documentation PAS is not fixed in order to be eligible.

27. Subject has COPD requiring continuous home oxygen therapy or chronic outpatient oral steroid use.
28. Subjects with non-cardiac comorbidities that are likely to result in a life expectancy of less than 12 months.
29. Modified Rankin Scale  $\geq 4$  disability.
30. Status 1 heart transplant or prior orthotopic heart transplantation.

31. Pregnant, lactating, or planning pregnancy during the clinical investigation follow-up period.

**Note:** Female subjects of childbearing age should be instructed to use safe contraception (e.g. intrauterine devices, hormonal contraceptives: contraceptive pills, implants, transdermal patches hormonal vaginal devices, injections with prolonged release).

32. Currently participating in an investigational drug or another device trial that has not reached its primary endpoint.

**Note:** Trials requiring extended follow-up for products that were investigational, but have since become commercially available, are not considered investigational trials.

33. Presence of other anatomic or comorbid conditions, or other medical, social, or psychological conditions that, in the investigator's opinion, could limit the subject's ability to participate in the clinical investigation or to comply with follow-up requirements, or impact the scientific soundness of the clinical investigation results.

### 5.3 Subject Selection

Subjects in this trial must have symptomatic, moderate-to-severe or severe mitral regurgitation or severe MAC. Subjects must be treated per standard of care, meet trial eligibility criteria, and have been assessed by the local site heart team for suitability for mitral valve surgery (see **Section 6 - Subject Screening and Randomization**). Several mechanisms will be employed in this trial to ensure appropriate subjects are registered in the trial:

- Subjects will be selected for inclusion in the SUMMIT trial by a multidisciplinary team at each investigational site involving interventional cardiology, cardiac surgery, imaging (echocardiography and CT) and heart failure personnel, as appropriate.
- All imaging (TEE, TTE, and Cardiac CT) will be submitted to the Sponsor and assessed by independent Echocardiography/CT Core Laboratories. The Sponsor (or imaging core laboratory) may provide echocardiographic and/or cardiac CT training/guidance to sites and assist in the review of screening images to ensure conformance to trial eligibility requirements.
- The SEC must concur with the local site heart team that subjects have been treated per standard of care, meet trial eligibility criteria, and can be treated in the Randomized, Non-repairable, Severe MAC or Severe MAC CAP cohorts of the trial (see **Section 12.11.2 - Subject Eligibility Committee** for more details).

### 5.4 Subject Registration

Subjects are enrolled in the trial upon providing written informed consent. For the Randomized cohort, subjects will be considered registered in the trial at the time of subject randomization. Sites may not register more than [REDACTED] of the total of [REDACTED] in the randomized cohort.

For the Non-repairable, Severe MAC and Severe MAC CAP cohorts, subjects are considered registered in the trial upon Tendyne procedure attempt (initial incision for the Tendyne procedure). Sites may not register more than [REDACTED] of the total subjects in the Non-repairable [REDACTED] or Severe MAC [REDACTED] cohorts.

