**Table 4. Anticipated Adverse Events (Tendyne Transcatheter Mitral Valve System)**

Adverse foreign body response	Foreign body response
Adverse reaction to anesthesia	Heart Failure, new or worsening
Allergic reaction	Hematoma
Anemia	Hemolysis
Annular dissection	Hypotension
Aortic insufficiency	Infection / sepsis
Atrial or ventricular injury	Leaflet, chordal, papillary or ventricular rupture (resulting from mitral valvuloplasty, if performed)
Atrial Septal Defect (resulting from mitral valvuloplasty, if performed)	Liver failure
Bioprosthetic valve dysfunction	Mitral valve injury
Bleeding complications	Mitral valve prolapse / stenosis
Blood loss which may require transfusion	Myocardial infarction
Cardiac arrest	Obstruction
Cardiac arrhythmia, Atrial or Ventricular	Pain
Cardiac perforation	Pleural effusion
Conduction defect, with or without need for pacemaker	Pulmonary embolism
Damage to cardiac tissue and/or structures	Pulmonary hypertension
Death	Paravalvular leak
Decreased LV function and/or cardiac output	Pericardial effusion / tamponade
Device embolism	Renal insufficiency or failure
Device erosion, migration or malposition	Respiratory difficulty, insufficiency or failure
Device thrombosis	Stroke or transient ischemic attack
Embolism (air, blood clot, calcium, tissue, etc.)	Tear or damage to device
Endocarditis	Vascular and access-related complications
Esophageal irritation, stricture, or perforation	Worsening of mitral regurgitation
Fever	

Normal postoperative sequelae or expected postoperative events during the acute perioperative period (72 hours) should not be recorded as SAEs unless they meet the seriousness criteria defined

in Section 9.1.2. A few common examples of normal post-operative sequelae or expected postoperative events include access-site pain, bruising, and events related to general anesthesia.

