## **9.4 Adverse Event / Device Deficiency Reporting**

### ***9.4.1 AE Reporting***

The investigator will monitor the occurrence of adverse events for each subject during the course of the trial. Event description, date of onset, severity, duration, and relationship to device and/or procedure will be recorded on the appropriate eCRF by the investigator or designee.

For subjects implanted with the Tendyne valve, a TTE must be conducted if signs or symptoms suggestive of valve dysfunction are exhibited. If the TTE indicates evidence of valve dysfunction, a cardiac CT must be performed. If renal insufficiency precludes a cardiac CT, a TEE must be performed instead.

For this clinical investigation, only SAEs, regardless of device and/or procedural relatedness, will be collected on each subject from the time of trial registration through trial completion. A summary of AE reporting requirements is further described in this section and summarized in

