### 10.1.2 Non-repairable, Severe MAC and Severe MAC CAP Cohorts

#### Attempted Procedure (AP) Population

The Attempted Procedure population for the Non-repairable and Severe MAC cohorts will consist of subjects in whom a Tendyne procedure is attempted.

[REDACTED]

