3.2 Adverse Events

All serious adverse device or procedure effects and UADEs will be summarized for all subjects who are randomized (ITT population of Randomized cohort) or underwent an attempted procedure (AP population for Non-repairable or Severe MAC Cohorts) in this trial in terms the number of events, the percentage of subjects with events. All CEC adjudicated adverse events will also be summarized similarly for all mITT, PP and AP populations. Moreover, COVID-19 related AEs will be summarized in terms of number of events, the percentage of subjects with events per MedDRA code.

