3.5.4 Device and Procedure-Related Endpoints

The following device and procedure-related acute endpoints will be reported:

- Implant Rate: defined as the rate of successful delivery and deployment of Tendyne device with retrieval of the delivery catheter
- Device Time: defined as the time elapsed from the start of the apex penetration to the time the tether tensioning ends

Statistical Analysis Plan

- Device Procedure Time: defined as the time elapsed from the first incision to the time of skin closure
- Total Procedure Time: defined as the time elapsed from the start time of anesthesia to time of skin closure
- Fluoroscopy duration: defined as the duration of exposure to fluoroscopy during the procedure

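### In the single-arm cohorts SAE collection opens at initial incision, so a serious procedural event that stops the case before incision is outside it, and the protocol conflicts on pre-incision events in subjects who go on to incision

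*Protocol*

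**What the plan says.** **Registration.** For the single-arm cohorts, Protocol 5.4 states that "subjects are considered registered in the trial upon Tendyne procedure attempt (initial incision for the Tendyne procedure". For the Randomized cohort, the same section states that "subjects will be considered registered in the trial at the time of subject randomization".

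**SAE window.** Protocol 9.4.1 states that "only SAEs, regardless of device and/or procedural relatedness, will be collected on each subject from the time of trial registration through trial completion".

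**Analysis set.** Protocol 10.1.2 says the AP population "will consist of subjects in whom a Tendyne procedure is attempted"; the text after that sentence is redacted, as is SAP 2.1.2.1. SAP 3.2 summarizes serious device or procedure effects in the single-arm cohorts for subjects who "underwent an attempted procedure (AP population for Non-repairable or Severe MAC Cohorts".

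**Subjects never registered.** Under Protocol 5.1 they are withdrawn, and the screening form keeps the reason for not registering. Under Protocol 5.5, only vital status is recorded after withdrawal.

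**Listed harms.** Table 4 includes "Adverse reaction to anesthesia" and esophageal injury up to perforation. The note under the table treats perioperative events, with general anesthesia as an example, as recordable SAEs when they are serious.

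**Schedule.** Appendix IV marks adverse events at the Procedure visit, whose window spans the time before and after implant. It does not mark them at Screening / Baseline. Protocol 7.4.3 lists adverse events among the procedural data.

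**Procedure times.** SAP 3.5.4 has "Total Procedure Time: defined as the time elapsed from the start time of anesthesia to time of skin closure", alongside two other times that start at first incision and at apex penetration.

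**The concern.** Anesthesia, TEE probe placement, and any line or catheter placed before the incision are parts of the Tendyne procedure. If one of them causes a serious event and the team stops before cutting, the subject is never registered. The event then has no SAE report, no three-day reporting deadline, no relatedness assessment and no route to adjudication. The subject also seems to belong to no analysis set.

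Two things are at stake. The first is the completeness of the procedural safety record in the three cohorts where every subject is meant to receive the device. The second is the 12-month performance-goal endpoint, which would omit a death before incision, and any later death or heart failure hospitalization in a subject whose case was abandoned.

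**Working it through.** The plan gives no figure to reproduce here. The check is mainly textual, with a short calculation for scale.

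**Case stopped before incision, single-arm cohort**

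1. No incision means no registration (Protocol 5.4).
2. No registration means SAE collection has not started (Protocol 9.4.1).
3. If attempt means incision, as 5.4 has it, the subject is not in the AP population. This step is an inference. Protocol 4.2 and the CAP definition in SAP VI.2.1.2 say only that a procedure is attempted.
4. The subject is withdrawn (5.1), and only vital status is recorded afterwards (5.5).

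**Same event, Randomized cohort.** Registration was at randomization, so the SAE window is open. Protocol 8.1 keeps a randomized subject without an implant procedure in follow-up. The event is captured.

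**Subject who reaches incision, with a serious event starting between anesthesia and incision.** Protocol 7.4.3, the note under Table 4 and Appendix IV point to recording it. Protocol 9.4.1, read literally, excludes it because onset precedes registration. The passages conflict.

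**Roll-in subjects.** Protocol 4.2 describes them as treated before subjects are registered in the cohorts, and 8.1 names them separately from registered subjects. A window that opens at registration gives them no defined start.

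**Effect on the primary estimate**

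Inputs: N = 103 and performance goal 43% (Severe MAC); N = 325 and performance goal 45% (Non-repairable); one-sided 2.5% level (Protocol 4.2, 10.2.2, 10.2.3). The event-free rate of 60% and the number k of omitted failures are assumptions. The shift from adding k omitted failures to x event-free subjects is x/N − x/(N + k).

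- Severe MAC, x = 62: 62/103 − 62/104 = 60.19% − 59.62% = 0.58 points for k = 1. For k = 5: 60.19% − 62/108 = 2.79 points.
- Non-repairable, x = 195: 195/325 − 195/326 = 60.00% − 59.82% = 0.18 points for k = 1. For k = 5: 60.00% − 195/330 = 0.91 points.
- An abandoned subject who is alive without heart failure hospitalization at 12 months would move the estimate up if added: 63/104 − 62/103 = 0.38 points, or 196/326 − 195/325 = 0.12 points.

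**Effect on the test.** This uses an exact binomial test as an approximation, because the planned method is partly redacted.

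- Severe MAC: success needs at least 55/103 (53.4%, p = 0.0215). One omitted failure gives 55/104, p = 0.0269, which no longer passes.
- Non-repairable: success needs at least 165/325 (50.8%, p = 0.0211). One omitted failure gives 165/326, p = 0.0240, which still passes. Two give 165/327, p = 0.0271, which does not.

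These reversals occur only when the observed result sits exactly on the success threshold.

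**The case against.** The strongest reply is that the gap is narrow and partly covered. Anesthesia and TEE continue after incision, so most of their harms fall inside the window, and listing them in Table 4 does not conflict with an incision start. Abandoned cases leave a trace: the reason for not registering is kept, and Protocol 13.5 collects eCRF data on all enrolled, that is consented, subjects. The incision boundary is also one that the SAP uses itself, since only one of its three procedure times starts at anesthesia. Finally, a rule for abandoned cases may stand in the redacted AP text.

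Most of this stands, and it limits the point. A reader might infer that all pre-incision anesthesia and TEE events go unrecorded. The documents do not support that: for subjects who reach incision they conflict, and that is not a clear exclusion. A reader might also infer that procedural safety is spoiled for a comparison between randomized Tendyne subjects and the single-arm cohorts. The plan evaluates the cohorts separately (Protocol 10.6, SAP 2.11) and states no such comparison. What the DSMB is shown is set in a charter that is not among the documents, so no claim about its data can be made.

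The reply does not close the gap for cases stopped before incision. A reason-for-not-registering entry is not an SAE report, and the general eCRF sentence does not override the specific window in 9.4.1. UADE reporting (Protocol 9.1.4) covers effects not previously identified in nature, severity or degree of incidence, and these harms are already listed as anticipated.

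**Conclusion.** The point holds in limited form. In the Non-repairable, Severe MAC and CAP cohorts, a serious procedural event that stops the case before incision is outside SAE collection by the stated rule. It is apparently outside the AP population too, subject to the redacted text. For subjects who reach incision, Protocol 9.4.1 conflicts with 7.4.3, the note under Table 4 and Appendix IV, and the passages must be reconciled. The SAE start for roll-ins is undefined; since roll-ins do not count toward the cohorts, this cannot affect a primary test.

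It is tempting to say that the omission always favours the device. It does not. A non-fatal esophageal or line complication is not a component of the primary endpoint, and leaving out an abandoned subject who does well works slightly against the device. Only pre-incision deaths, or later death or heart failure hospitalization in abandoned subjects, favour it. It is also tempting to put the cost of one omitted death at 1/103 = 1.0 point and 1/325 = 0.3 point. Those figures apply when a counted success becomes a failure. Here a failure is added to the denominator, and at an assumed 60% event-free rate the shift is about 0.6 and 0.2 points.

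No document gives a rate for such events, so their expected number is unknown. The reason to act is completeness of the safety record; the effect on the performance-goal tests is likely to be small.

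**What to change.** - **Protocol 9.4.1:** for the Non-repairable, Severe MAC, CAP and roll-in subjects, start SAE collection no later than the start of anesthesia for the Tendyne procedure. Align 7.4.3, the note under Table 4 and Appendix IV with that start.
- **SAP 3.2 and VI.3.2:** list every case with anesthesia started and no incision, with its SAEs and vital status.
- **SAP 2.13:** keep the AP population as primary and add one sensitivity analysis of the primary endpoint that includes these cases, with a descriptive counterpart for CAP in VI.2.11. Because Protocol 5.1 withdraws unregistered subjects, their heart failure hospitalizations may be unknown. State in advance how such a subject is counted, for example as a failure in a worst-case version.

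Registration and the AP population need not be redefined. That is a debatable design choice, and the gap closes without it.

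The cost is protocol and SAP wording and a little extra data collection. Anesthesia start time is already needed for Total Procedure Time. The sensitivity estimate may come out slightly less favourable than the primary one.
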